#### 4.3.4.3 Exploratory Endpoints

To estimate ORR, DOR, DCR, TTP, and PFS per iRECIST by M.D. Anderson radiology per iRECIST, instead of per RECIST 1.1.

Tissue and blood immune monitoring will be conducted through our immune platform group as details per the biomarker section based on 3 biopsies done at the following time points: 1) pre-treatment, 2) 6 weeks after therapy, and 3) an optional biopsy upon progression.

#### 4.3.4.4 Modified RECIST 1.1 for Immune-based Therapeutics (iRECIST)

RECIST 1.1 will be adapted to account for the unique tumor response characteristics seen following treatment with pembrolizumab (Section 7.1.4.1.5). Immunotherapeutic agents such as pembrolizumab may produce antitumor effects by potentiating endogenous cancer-specific immune responses. The response patterns seen with such an approach may extend beyond the typical time course of responses seen with cytotoxic agents, and patients treated with pembrolizumab may manifest a clinical response after an initial increase in tumor burden or even the appearance of new lesions. Thus, standard RECIST 1.1 may, not provide an accurate response assessment of immunotherapeutic agents such as pembrolizumab. Based on an analysis of subjects with melanoma enrolled in KN001, 7% of evaluable subjects experienced delayed or early tumor pseudo-progression. Of note, subjects who had PD by RECIST 1.1 but not by the immune-related response criteria (90) had longer OS than subjects with PD by both criteria (91). Additionally, the data suggest that RECIST 1.1 may underestimate the benefit of pembrolizumab in approximately 15% of subjects. These findings support the need to apply a modification to RECIST 1.1 that takes into account the unique patterns of atypical responses in immunotherapy and enables treatment beyond initial radiographic progression, if the subject is clinically stable.

iRECIST assessment has been developed and published by the RECIST Working Group, with input from leading experts from industry and academia, along with participation from the US Food and Drug Administration and the European Medicines Agency (92). The unidimensional measurement of target lesions, qualitative assessment of non-target lesions, and response categories are identical to RECIST 1.1, until progression is seen by RECIST 1.1. However, if

# Proprietary Information of MD Anderson

Protocol # 2016-0251

Date: February 24, 2020

34

a subject is clinically stable, additional imaging may be performed to confirm radiographic progression. iRECIST will be used by Investigators to assess tumor response and progression and make treatment decisions as well as for exploratory efficacy analyses where specified.

iRECIST will be used by M.D. Anderson Cancer Center (MDACC) investigators to assess tumor response and progression, and make treatment decisions as well as by M.D. Anderson Department of Diagnostic Imaging in support of all secondary and exploratory response endpoints. Confirmation of PD for iRECIST endpoints will be taken from central imaging (this will be done by Quantitative Imaging Analysis Core [QIAC] at MDACC) retrospectively, according to iRECIST definition.

## 4.3.4.5 Safety Endpoints

Safety parameters commonly used for evaluating investigational systemic anticancer treatments are included as safety endpoints including, but not limited to, the incidence of, causality, and outcome of adverse events (AEs)/serious adverse events (SAEs); and changes in vital signs and laboratory values. Adverse events will be assessed as defined by CTCAE, Version [4.0].

## 4.3.4.6 Biomarker Research

Cancer immunotherapies represent an important and novel class of antitumor agents. However, the mechanism of action of these exciting new therapies is not completely understood and much remains to be learned regarding how best to utilize these new drugs in treating patients. Thus, to aid future patients, it is important to investigate the determinants of response or resistance to cancer immunotherapy, as well as determinants of AEs in the course of our clinical trials. These efforts will identify novel predictive/PD biomarkers and generate information that will better guide single-agent and combination therapy with immunotherapy drugs. To identify novel biomarkers, biospecimens (ie, blood components, tumor material) will be collected to support analyses of cellular components (eg, protein, DNA, RNA, metabolites) and other circulating molecules. Translational studies to be performed on tissue and blood will be detailed in a separate procedure manual.

## Sample Collection

- CNB samples:** A new fresh CNB will be obtained in all subjects prior to treatment (15 samples), 6 weeks after treatment has commenced, and an optional CNB biopsy upon progression. At least 5 cores will be obtained from the CNB procedure. The CNB cores (~6-8 mm in length) will be processed as FFPE or fresh frozen specimens. The CNB specimens will be examined for quality control and pathological characterization before being utilized for immune-profiling, as well as for DNA, RNA, protein extractions and flow cytometry. These samples will be stored at -80°C.

# Proprietary Information of MD Anderson

Protocol # 2016-0251

Date: February 24, 2020

35

2. Blood specimens: Blood collection will be performed at screening, pre-chemo at Week 3 (end of Cycle 1), Week 6 (end of Cycle 2), and at confirmation of progressive disease/end of treatment. Depending on response, 3 to 4 blood samples will be collected per subject. There will be up to a total of 120 blood samples (15 patients  $\times$  4 samples  $\times$  2 arms = 120 blood samples), which will be collected in 3 CPT- and 2 purple-top tubes.

Three Vacutainer Cell Preparation Tubes (CPT) tubes, 8 ml of blood each with sodium heparin (Becton Dickinson Cat # 362753) will be processed for PBMCs isolation and cryopreserved. PBMCs will be isolated from blood at MDACC Institutional Tissue Bank (ITB). PBMC samples will then be submitted to Biostorage for flow cytometry analyses at Merck. Plasma from these three CPT tubes will be collected and frozen and sent to Biostorage for future use as determined by the Joint Steering Committee.

For TCR analysis, both purple top EDTA tubes of blood (20 ml total) will be processed for PMBCs isolation at MDACC ITB and will be shipped to MDACC TMP for genomic DNA extraction. For liquid biopsy analyses, plasma will be collected from the one EDTA tube being used to make genomic DNA (above) as well as a second EDTA tube (10 ml). These plasma samples will be frozen for future genotyping analysis of circulating free DNA (cfDNA) and/or circulating tumor cells (CTCs) at MDACC MTDL.

Investigations may include but are not limited to:

## Blood Analysis

Subjects will have peripheral blood collected at pre-treatment, Week 6, time of response, and time of progression/end of study for both Arm 1 and Arm 2.

Flow cytometry: High order flow cytometry panels will be designed with input from the investigators and Merck at the time of analysis. The panels may include but not be limited to: 1) delineation of major immune cell types (T cells, B cells, NK cells, DCs, MDSCs), 2) determination of T cell differentiation status and limited functionality (IFNg, tumor necrosis factor alpha [TNF $\alpha$ ], GB) and 3) defining the expression level of costimulatory and coinhibitory molecules on T cells and myeloid cells. The proposed studies will be conducted on cryopreserved PBMCs.

Liquid Biopsy Analysis (optional): Using plasma specimens, genotyping analysis of circulating free DNA (cfDNA), circulating tumor cells (CTCs), and exosome (exo)-DNA may be performed to monitor tumor response and progression at the Molecular Testing Developmental Laboratory (MTDL; [name] and [name]) housed in TMP.

Serum Cytokine Analysis (optional): Serum cytokines to be measured may include IFN- $\gamma$ , GB, perforin, IL-10, CCL20/MIP3 $\alpha$ , and CXCL12/SDF-1. Additional cytokine panels may be selected at the discretion of the investigators or Merck based on emerging literature.

T cell receptor (TCR) Analysis: TCR sequencing analysis will be performed using DNA from PBMC. Total T cell density, TCR diversity and clonality will be evaluated. TCR profile

# Proprietary Information of MD Anderson

Protocol # 2016-0251

Date: February 24, 2020

36

generated from treatment-refractory tumors at the time of PD will be compared to data from pre-treatment tumor samples to explore the TCR repertoire evolution of these tumors under therapeutic pressure. TCR profile will be correlated to clinical response as well as genomic profile of the tumor.

Blood will also be obtained for HCV viral load using the COBAS assay.

## HCV Markers

COBAS AmpliPrep/COBAS TaqMan HCV Test, v2.0 will be performed according to the manufacturers instructions. The key end point fore the HCV kinetics and response to Zepatier will be the COBAS test.

HCV resistance GTs will be assessed across the entire NS3/4A and NS5A regions for all subjects as per standard clinical testing for resistance .

## Tissue Analysis

Tissue immune monitoring will be conducted done at the following time points: 1) pre-treatment, 2) 6 weeks after therapy, and 3) an optional biopsy upon progression.

The analyses will be performed at M.D. Anderson Tissue Molecular Pathology laboratory – in particular, the immunoprofiling lab (TMPIL) directed by [name] and a Merck research Laboratories. Assays may include but are not be limited to:

## Tumor PD-L1 Expression

In the pembrolizumab PN001 and PN012 studies, PD-L1 IHC has successfully been used as a biomarker in the NSCLC to enrich for a subpopulation with high response to pembrolizumab. Therefore, the relationship between PD-L1 expression in tumor tissue and response to treatment with pembrolizumab will be evaluated. PD-L1 expression in tumor cells and inflammatory cells within pre-treatment tumor tissue samples will be characterized by IHC and retrospectively tested for association with response to pembrolizumab. The range of PD-L1 staining in a population of HCC tumors may also be used to identify a cut-off, above which a tissue is scored as biomarker positive.

## Multiplex Immunofluorescence Analysis (MIF)

MIF may be performed on tumor core samples utilizing immune marker panels. The panels to be utilized will be developed in collaboration and agreement with Merck Research Laboratories and MD Andesron. MIF panels will interrogate tumor, immune cell infiltrates, and stromal components of the tumor.

## Immune-related Gene Expression Profile

Intratumoral expression levels of select genes may be analyzed using an analytically validated platform, such as the NanoString nCounter Analysis System. Association between the

# Proprietary Information of MD Anderson

Protocol # 2016-0251

Date: February 24, 2020

37

immune-related GEP and response to pembrolizumab has been established using these genes in melanoma and in cancers from clinical studies KN012 (head and neck, bladder, and gastric cancers) and KN028 (ovarian, esophageal, and other cancers). Data from these cohorts has been used to derive a GEP which combines the expression levels of several key genes into a single scalar score. The pattern of association in the esophageal cohort of KN028 using a prototype GEP suggested the ability to identify patients who may not respond to pembrolizumab by identifying tumors that have low values of the GEP. The GEP includes genes from immune-regulatory pathways and a GEP score will be tested for association with response to pembrolizumab in retrospective fashion. The relationship between GEP and the probability of response will be used to develop cut-offs that may have high clinical utility.

These Nanostring analyses will be performed using FFPE tissue from the core needle biopsy (CNB) specimens at Merck's vendor of choice.

## **Global Transcriptional Analyses**

In addition to examining an immune-related GEP described above, RNA-Seq global messenger RNA profiling will also be pursued. RNAseq wil be performed on fresh core biopsies at a vendor of Merck's choice. Expression of individual genes related to the immune system may also be evaluated such as immune signatures and critical cytokines (e.g., IL-10).

## **Genetic (DNA) Analyses from Tumor**

The application of new technologies, such as next generation sequencing, has provided scientists the opportunity to identify tumor-specific DNA changes (ie, mutations, methylation status, microsatellite instability). Key molecular changes of interest to immune-oncology drug development include the mutational burden of tumors and the clonality of T cells in the tumor microenvironment. Increased mutational burden (sometimes referred to as a "hyper-mutated" state) may generate neo-antigen presentation in the tumor microenvironment. To conduct this type of research, it is important to identify tumor-specific mutations that occur across all genes in the tumor genome. Thus, genome-wide approaches may be used for this effort. Note that in order to understand tumor-specific mutations; it is necessary to compare the tumor genome with the germline genome. Microsatellite instability may also be evaluated as this is an important biomarker for some cancers (ie, colorectal cancer)..

## **Whole Exome Sequencing**

Flash freezing of fresh biopsy cores in liquid nitrogen may allow for RNA-squencing and Whole Exome Sequencing of tumor. This analysis will be performed using fresh frozen tissue specimens from CNB tumor tissues at Merck.

For all biomarker analyses, please refer to laboratory manuals for further details.

## **Planned Genetic Analysis**

Understanding genetic determinants of drug response is an important endeavor during medical research. This research will evaluate whether genetic variation within a clinical trial

# Proprietary Information of MD Anderson

Protocol # 2016-0251

Date: February 24, 2020

38

population correlates with response to the treatment(s) under evaluation. If genetic variation is found to predict efficacy or adverse events, the data might identify optimal use of therapies in the patient population. This research contributes to understanding genetic determinants of efficacy and safety associated with the treatments in this study.

## 4.3 Benefit/Risk

Subjects in clinical trials may not receive direct benefit from treatment during participation, as clinical trials are designed to provide information about the safety and effectiveness of an investigational medicine. However, data using similar drugs in HCC and other cancers suggests that some subjects may benefit from therapy.

Additional details regarding specific benefits and risks for subjects participating in this clinical trial may be found in the accompanying IB and Informed Consent documents.

## 5.0 METHODOLOGY

### 5.1 Entry Criteria

#### 5.1.1 Diagnosis/Condition for Entry into the Trial

For Arm 1 and 2 male and female subjects with advanced HCC with no curative option [of at least 18 years of age](#) will be enrolled in this trial.

For Arm 2 male and female subjects that are HCV-positive with genotype 1 or 4 virus infection will be enrolled.

#### 5.1.2 Subject Inclusion Criteria

In order to be eligible for participation in this trial, the subject must:

1. Be willing and able to provide written informed consent for the trial. The subject may also provide consent for Future Biomedical Research (FBR). However, the subject may participate in the main trial without participating in FBR.
2. Be at least 18 years of age on the day of signing informed consent.
3. Have histologically or cytologically confirmed diagnosis of HCC (fibrolamellar and mixed hepatocellular/cholangiocarcinoma subtypes are not eligible) based on pathology report.
4. For Arm A and B: have Barcelona Clinic Liver Cancer (BCLC) Stage C disease or BCLC Stage B disease not amenable to locoregional therapy or refractory to locoregional therapy, and not amenable to a curative treatment approach (see Section 12.9).
5. For Arm B have a detectable GT1, GT4, or HCV viral load TD(q) based on the Roche COBAS AmpliPrep/COBAS TaqMan HCV Test, v2.0 from a blood sample. HCV

# Proprietary Information of MD Anderson

Protocol # 2016-0251

Date: February 24, 2020

39

RNA ( $\geq 10,000$  IU/mL in peripheral blood) at the time of screening have documented chronic HCV GT1, GT4 (with no evidence of mixed genotype) infection:

- a. Positive for anti-HCV antibody, HCV RNA, or any of the above HCV GTs at least 3 months before screening (HCV RNA and HCV GT must be confirmed by screening lab results) OR
- b. Positive for anti-HCV antibody or HCV RNA at the time of screening with a liver biopsy consistent with chronic HCV infection (or a liver biopsy performed before enrollment with evidence of CHC disease, such as the presence of fibrosis) or a Fibroscan performed within 12 months of Day 1 of this study with a result of  $>12.5$  kPa or a FibroSure® (Fibrotest®) performed during Screening with a score of  $>0.75$  and an aspartate aminotransferase (AST): platelet ratio index (APRI) of  $>2$ . APRI formula:  $AST \div \text{lab upper limit of normal (ULN)} \text{ for } AST \times 100 \div \{\text{platelet count} \div 100\}$  (APRI calculation to be provided by the central laboratory.)
6. For Arm B subjects must undergo at screening HCV GT1a testing for resistance polymorphism as per Zepatier label.
7. Have a Child-Pugh A liver score at screening or within 14 days of first dose of study drug.
8. For Arm B have liver disease staging assessment as follows:

## **Cirrhosis is defined as any one of the following**

- a. A liver biopsy performed prior to Day 1 of this study showing cirrhosis (F4)
- b. Fibroscan performed within 12 calendar months of Day 1 of this study showing cirrhosis with result  $>12.5$  kPa [29]\*
- c. A FibroSure® (Fibrotest®) performed during Screening with a score of  $>0.75$  and an aspartate aminotransferase (AST): platelet ratio index (APRI) of  $>2$ . APRI formula:  $AST \div \text{lab upper limit of normal (ULN)} \text{ for } AST \times 100 \div \{\text{platelet count} \div 100\}$  (APRI calculation to be provided by the central laboratory.)

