## **Absence of cirrhosis is defined as any one of the following:**

- a. Liver biopsy performed within 24 months of Day 1 of this study showing absence of cirrhosis
- b. Fibroscan performed within 12 months of Day 1 of this study with a result of  $\leq 12.5$  kPa [29]\*
- c. A FibroSure (Fibrotest) score of  $\leq 0.48$  and AST to Platelet Ratio Index (APRI) of  $\leq 1$  during Screening

Fibroscan cut-off of 12.5 kPa has a positive predictive value of 90% and a sensitivity of 95% for  $\geq F3$ . Based on box and whisker plot of interquartile distribution  $>12.5$  kPa will exclude the majority of subjects with metavir F3 fibrosis. In the absence of a definitive diagnosis of presence or absence of

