# Proprietary Information of MD Anderson

Protocol # 2016-0251

Date: February 24, 2020

40

cirrhosis by the above criteria, a liver biopsy is required. Liver biopsy results supersede the results obtained by Fibroscan or Fibrosure.

9. Have a predicted life expectancy of greater than 3 months.
10. Have measurable disease based on RECIST 1.1 as confirmed by the blinded M.D. Anderson radiology. Target lesions situated in a previously irradiated area are considered measurable if progression has been demonstrated in such lesions.

Note: the same image acquisition and processing parameters should be used throughout the study for a given subject..

11. Have a performance status of 0 or 1 using the ECOG Performance Scale within 7 days of first dose of study drug.
12. Have documented objective radiographic progression after stopping treatment with sorafenib or else intolerance to sorafenib. Intolerance to sorafenib is defined as: NCI CTCAE version 4.0 (Section 12.4) Grade  $\geq 2$  drug-related AE(s) which both a) persisted in spite of comprehensive supportive therapy according to institutional standards and b) persisted or recurred after sorafenib treatment interruption of at least 7 days and dose reduction by one dose level. Patients treated on sorafenib as the last treatment may start pembrolizumab at least 14 days after the last dose of sorafenib.
13. For Arm B Subjects with chronic active infection by HCV who are untreated or treated are allowed on study
14. Subjects with a past or resolved hepatitis B virus (HBV) infection, defined as having a negative HBsAg test and a positive total hepatitis B core antibody (HBcAb) test and negative HBV DNA test at screening, are eligible for the study.
15. Female subjects of childbearing potential must have a negative urine or serum pregnancy test within 72 hours prior to receiving the first dose of trial medication. If the urine test is positive or cannot be confirmed as negative, a serum pregnancy test will be required.
16. Male subjects of childbearing potential must agree to use an adequate method of contraception as outlined in Section 5.6.3 - Contraception, starting with the first dose of trial therapy through 120 days (Arm A) or 180 days (Arm b) after the last dose of trial therapy.

Note: Abstinence is acceptable if this is the usual lifestyle and preferred contraception for the subject.

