# Proprietary Information of MD Anderson

Protocol # 2016-0251

Date: February 24, 2020

41

- c. contraceptive rod implanted into the skin

Combination method (requires use of 2 of the following):

- d. diaphragm with spermicide (cannot be used in conjunction with cervical cap/spermicide)
- e. cervical cap with spermicide (nulliparous women only)
- f. contraceptive sponge (nulliparous women only)
- g. male condom or female condom (cannot be used together)
- h. hormonal contraceptive: oral contraceptive pill (estrogen/ progestin pill or progestin- only pill), contraceptive skin patch, vaginal contraceptive ring, or subcutaneous contraceptive injection

Note: Abstinence (relative to heterosexual activity) can be used as the sole method of contraception if it is consistently employed as the subject's preferred and usual lifestyle and if considered acceptable by local regulatory agencies and Institutional Review Boards (IRBs)/Ethics Review Committees (ERCs). Periodic abstinence (e.g., calendar, ovulation, sympto-thermal, post-ovulation methods, etc.) and withdrawal are not acceptable methods of contraception.

If a contraceptive method listed above is restricted by local regulations/guidelines, then it does not qualify as an acceptable method of contraception for subjects participating at sites in this country/region.

18. Subjects in Arm B treated with RBV must agree to double barrier birth control from Day 1 to 6 months following last dose of study therapy or they are excluded from this trial.

19. Have adequate organ function as defined in [Table 2](#). Specimens must be collected within 7 days prior to the start of trial treatment.

Table 2 Adequate Organ Function Laboratory Tests

System	Laboratory Value	
Hematological		
Absolute neutrophil count	$\geq 1500/\mu\text{L}$	
Platelets	$\geq 100,000/\mu\text{L}$	
Hemoglobin	$\geq 9.0 \text{ g/dL}$ or $\geq 5.6 \text{ mmol/L}^a$	
Renal		
Creatinine	OR $\leq 1.5 \times \text{ULN}$ OR Measured or calculated b creatinine clearance (GFR can also be used in place of creatinine or CrCl)	$\geq 30 \text{ mL/min}$ for subject with creatinine levels $>1.5 \times \text{institutional ULN}$
Hepatic		
Total bilirubin	$\leq 1.5 \times \text{ULN}$ OR direct bilirubin $\leq \text{ULN}$ for subjects with total bilirubin levels $>1.5 \times \text{ULN}$	
AST (SGOT) and ALT (SGPT)	$\leq 2.5 \times \text{ULN}$ ( $\leq 5 \times \text{ULN}$ for subjects with liver metastases)	

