# Proprietary Information of MD Anderson

Protocol # 2016-0251

Date: February 24, 2020

120

- GT (1a, 1 non-a, 4)
- Stage of fibrosis (Non-cirrhotic vs. Cirrhotic)
- *IL28B* CC genotype vs. non-CC genotype
- HCV RNA at baseline, low ( $\leq 800,000$  IU/mL) versus high ( $> 800,000$  IU/mL)
- IFN treatment eligibility status (eligible or ineligible)

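### The APRI formula printed in inclusion criteria 5b and 8 does not fit the protocol's own cut-offs of >2 and ≤1, and its platelet unit is not stated

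*Combined protocol and SAP*

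**What the plan says.** Section 5.1.2 uses the index in three places for Arm B.

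- **Inclusion 5b** (one route to documenting chronic HCV) accepts a biopsy, a Fibroscan above 12.5 kPa, or FibroSure above 0.75 together with APRI above 2.
- **Inclusion 8, cirrhosis** accepts any one of biopsy, Fibroscan above 12.5 kPa, or the same FibroSure/APRI pair.
- **Inclusion 8, absence of cirrhosis** accepts any one of biopsy, Fibroscan at or below 12.5 kPa, or FibroSure at or below 0.48 with "AST to Platelet Ratio Index (APRI) of $\leq 1$ during Screening".

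The formula is printed identically in 5b and in the cirrhosis definition. After dividing AST by its ULN it continues, in the document's notation, "AST \times 100 \div \{\text{platelet count} \div 100". No platelet unit is given. Both places add "APRI calculation to be provided by the central laboratory".

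Where neither presence nor absence is settled, the rule is "cirrhosis by the above criteria, a liver biopsy is required", and biopsy overrides the other tests. Section 8.13.4 uses the resulting status as an SVR12 subgroup: "Stage of fibrosis (Non-cirrhotic vs. Cirrhotic".

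The flow chart in Section 6.1 lists Fibrotest and APRI at screening under the local laboratory heading, ahead of the central one.

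**The concern.** An index with cut-offs at 1 and 2 is useful only if eligible subjects can fall on either side of them. Table 2 restricts both components: platelets must be at least 100,000/µL, and AST at most 2.5 × ULN, or 5 × ULN "for subjects with liver metastases". The extra division of the platelet count by 100 appears to push the index well away from both cut-offs, in opposite directions depending on the unit.

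If so, the APRI half of each FibroSure/APRI criterion carries no information. At stake are how a subject's cirrhosis status is assigned, whether that status can be settled without a biopsy, one option for documenting chronic HCV, and the composition of a subgroup in an arm of about 15 subjects. One relabelled subject there is 1/15 = 6.7% of the arm.

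**Working it through.** The protocol gives no worked APRI value to reproduce, so the check evaluates the printed formula over the eligible range.

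**Inputs from the protocol.** The formula (inclusion 5b and 8); cut-offs >2 and ≤1 (inclusion 8); platelets ≥100,000/µL, which is ≥100 × 10⁹/L, and AST ≤2.5 × ULN or ≤5 × ULN (Table 2).

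**Assumed, not in the protocol.** AST no lower than 0.5 × ULN and platelets no higher than 400 × 10⁹/L, with a wider check down to 0.2 × ULN and up to 1000 × 10⁹/L. The per-µL result needs none of these assumptions.

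**Step 1: simplify.** With R = AST/ULN and P = platelet count, the printed index is R × 100 / (P/100) = 10,000 R / P.

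**Step 2: platelets per µL (the unit in Table 2).** The largest value occurs at P = 100,000.
- R = 2.5: 10,000 × 2.5 / 100,000 = 0.25.
- R = 5: 10,000 × 5 / 100,000 = 0.50.
- To exceed 2, R must be above 2 × 100,000 / 10,000 = 20.

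Every eligible subject is ≤1 and none is >2.

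**Step 3: platelets in 10⁹/L.**
- R = 1, P = 100: 10,000 / 100 = 100.
- R = 0.5, P = 400: 5,000 / 400 = 12.5, the minimum over the main assumed range.
- R = 5, P = 100: 50,000 / 100 = 500, the maximum.
- R = 0.2, P = 450: 2,000 / 450 = 4.4.
- To reach ≤1 at P = 400, R must be at most 400 / 10,000 = 0.04.

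Only at the far corner of the wider range (R = 0.2, P = 1000) does the index fall to 2,000 / 1,000 = 2.0. In practice every subject is >2 and none is ≤1.

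**Step 4: other readings of the operators.** If the 100 multiplies the ULN, or if the braces are ignored, the index becomes R / P. Its maximum is 5 / 100 = 0.05 in 10⁹/L and smaller per µL. Neither reading reaches either cut-off.

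**Step 5: consequence if applied as printed.**

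| Platelet unit | Cirrhosis branch (FibroSure >0.75 and APRI >2) | Absence branch (FibroSure ≤0.48 and APRI ≤1) |
|---|---|---|
| per µL | unreachable | decided by FibroSure alone |
| 10⁹/L | decided by FibroSure alone | unreachable in practice |

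The FibroSure/APRI option of 5b behaves like the cirrhosis branch.

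**Step 6: an assumed correction.** The documents print no other formula. Take 100 R / P with P in 10⁹/L, which is the same as dividing a per-µL count by 1000 instead of 100.
- R = 0.5, P = 400: 50 / 400 = 0.125.
- R = 5, P = 100: 500 / 100 = 5.0.

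The range now spans both cut-offs. The cirrhosis branch is still narrow: at R = 2.5, exceeding 2 needs P below 250 / 2 = 125 × 10⁹/L, against an entry floor of 100. The value 5.0 arises only under the liver-metastases allowance.

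**The case against.** The strongest reply is that the protocol does not ask sites to use the printed formula: the criterion assigns the calculation to the central laboratory, and the documents do not show which formula that laboratory uses. This stands in part, because harm requires the text to be applied literally. The safeguard is weakened by the flow chart, which places Fibrotest and APRI among local assessments, and by the absence of any other formula.

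A reader might also infer more than the documents support.

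- **That the FibroSure/APRI route is unusable.** It is not: in each unit one branch is lost and the other still works, on FibroSure alone.
- **That biopsies are forced.** Fibroscan classifies at a single threshold with no gap, and an earlier biopsy can also settle the status. A biopsy becomes required only where neither does. Fibroscan has no row in the flow chart, however, so the FibroSure/APRI pair is the non-invasive staging that is actually scheduled at screening.
- **That subjects are necessarily mislabelled.** APRI never classifies alone. An error needs FibroSure to be decisive and a properly scaled APRI to disagree with it. Nothing in the documents allows that frequency to be estimated.
- **That treatment is affected.** Table 4 sets Zepatier duration with or without cirrhosis.
- **That eligibility turns on it.** 5b is an alternative to 5a and itself offers biopsy or Fibroscan.

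Finally, a correct formula would not remove every indeterminate result: FibroSure above 0.48 and up to 0.75, or APRI above 1 and up to 2, stays unresolved by this route.

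**Conclusion.** The inconsistency is certain; its practical effect is conditional. Under Table 2's limits the printed index is at most 0.25 (0.50 with liver metastases) with platelets per µL, and about 12.5 to 500 with platelets in 10⁹/L over the assumed ranges, against cut-offs of 1 and 2. No usual unit or reading of the operators lets it discriminate. The per-µL figures rest only on the protocol; the 10⁹/L range also rests on the assumed lower AST and upper platelet limits, although widening them does not bring ≤1 within reach.

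If the formula is used as printed, the exposure is confined to cirrhosis staging, the FibroSure/APRI option of 5b, and one of six descriptive SVR12 subgroups. The overall SVR12 estimate does not depend on cirrhosis status. It should be corrected because it is a wrong rule in an entry and staging criterion, but the documents do not show that anyone has been biopsied or misclassified because of it.

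**What to change.** 1. In inclusion 5b and in the cirrhosis definition of inclusion 8, replace the formula with one that works with the >2 and ≤1 cut-offs, and state the platelet unit. An assumed form is (AST/ULN for AST) × 100 / platelet count in 10⁹/L; confirm it against the formula the laboratory reports before adopting it.
2. State once who calculates APRI, so that the central-laboratory note in Section 5.1.2 agrees with the flow chart in Section 6.1.
3. If any Arm B subject has already been staged by FibroSure/APRI, check which formula and unit were used before the SVR12 cirrhosis subgroup is tabulated.

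The cost is a short amendment in two criteria plus one flow-chart reconciliation. No change to sample size, endpoints or analysis methods is needed.
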